## **Double Blind Trial Investigating the Role of Sulfasalazine in Decreasing Opioids Requirements in Breast Cancer Patients**

### **Brief Summary**

Cancer pain in general, and cancer-induced bone pain in particular, is a significant health problem in the USA and the rest of the world. With the improvement of new surgical approaches and chemotherapies to treat manage cancer, the number of patients with cancer are now living longer. This great achievement created an unexpected problem. For some cancer patients with bone metastases, pain is worse than the cancer itself. The golden standard to manage cancer-induced bone pain is opioids. Patients with cancer-induced bone pain are now taking ever-increasing doses of opioids to control their pain. Sadly, opioids come with significant side effects. These side effects limit the amount of opioids that can be safely administered. Many attempts have been tried to create better regiments for pain control to lower the need for opioids. There has not been significant success in that area. A better approach to better control cancer-induced bone pain and lower the amount of opioids used would be to add a non-opioid agent that has a different mechanism of action(s). This may create synergism to better control pain while lowering the doses of opioids needed and lowering side effects. Sulfasalazine poses such quality. It is an anti-inflammatory drug with established safety profile. It has been in use for over fifty years for the treatment of inflammatory conditions such as rheumatoid arthritis. In addition to its anti-inflammatory characteristics, sulfasalazine has the capacity in decrease the survival of cancer cells and also to lower the amount of inflammatory mediators released by cancer cells. In short, sulfasalazine inhibits the influx of cysteine into cancer cells and the efflux of glutamate from cancer cells. Cysteine is needed for cell survival against oxidative stress, while glutamate activate pain receptors. Therefore, sulfasalazine will act as anti-inflammatory, an agent to accelerate cancer cells death, and decreasing the released glutamate which activate pain receptors. This one agent with three mechanisms of actions may lower the amount of opioid needed for cancer patients with cancer-induced bone pain while maintaining or improving their pain control. Lowering of opioid dosing may also decrease the side effects associated with opioid use which in turn may improve their quality of life. The objective of this clinical trial is to co-administer sulfasalazine with opioids to patients with cancer-induced bone pain and characterize their pain and their opioid use. Our hypothesis is that adding sulfasalazine to the pain medication regimen will lower the amount of opioids used and lower the side effects. This may improve the quality of life for cancer-induced bone pain patients and decrease the risks of using high amount of opioids for the patients, their families, and society in general. The primary objective of this study is to decrease the amount of opioid pain medication use after addition of sulfasalazine for 12 weeks while controlling pain. The secondary objective is to decrease the intensity of pain and increase the quality of life.

### **Study Description**

This double-blind clinical trial is intended for patients with moderate to severe cancer-induced bone pain on stable doses of opioids. This study is expected to last 12 weeks from the time a

## **Double Blind Trial Investigating the Role of Sulfasalazine in Decreasing Opioids Requirements in Breast Cancer Patients**

patient first receives the assigned treatment. Each patient will have 7 clinic visits that are related to the study. Initially, we will conduct urine pregnancy test before the start of the study and at week 6 except for patients with documented hysterectomies. If a patient suspects she may be pregnant, additional urine pregnancy test will be conducted. If the results suggest possible pregnancy, the patient will be excluded from the study.

Patients with breast cancer-induced bone pain will be identified and recruited from the chronic pain clinic and from the oncology clinic at the University of Arizona. The consent process as well as the pain evaluation will be conducted at the Chronic Pain clinic at South Campus or at the oncology clinic at main campus. Patients that meet our inclusion criteria and consent to the study will be randomized into either a placebo (sugar pill) or sulfasalazine group. We estimate that a sample size of 16 subjects per group will be necessary based on the power calculations shown below. Because not all subjects will complete the study and provide evaluable data, we will enroll 20 subjects per group. Forty patients will be stratified according to age and randomly assigned to either a placebo or active treatment group in a 1:1 ratio. The randomization sequence will be generated by the Biostatistics Shared Resource of UACC using a computer-generated process. The assignment of patients will be revealed only to the pharmacist. The pharmacist will also not be involved in communicating with patients or analyzing the data. Neither the patients nor the treating physicians will know into which group individual patients will be assigned. Initially, all patients will be given written surveys designed to assess for opioid use, pain level, and quality of life.

The treatment group will receive supplies for 3 months of sulfasalazine at an initial dose of 0.5 gram three times a day for a week then at a dose of 1 gram three times a day for the remainder of the 3 months. Patients will be asked to take their medications with every meal (assuming three meals a day) in addition to their regular pain medications. The placebo group will be asked to take capsules filled with cornstarch three times a day in a similar manner.

The patients will return to the pain clinic or the oncology clinic for follow ups at 2 weeks (+/- 1 week), 4 weeks (+/- 1 weeks), 6 weeks (+/- 1 weeks), and 8 weeks (+/- 1 week), 10 weeks (+/- 1 week), and 12 weeks (+/- 1 week) at which times all follow-up measures from the surveys will be collected. Additionally, a physical exam will be performed on every patient at every follow up appointment. The physical examination will be focusing on the mental status by asking Mini Mental State test. We will also examine the abdomen by light and deep palpation. Any deviation from the normal limits will result in un-blinding the effected patient (to elucidate whether he/she is a control or a treatment group) and withdrawal from the study. If intestinal or urinary obstruction is suspected, the appropriate imaging studies will be conducted and a consultation with the appropriate surgical service will be requested if indicated.

The following is a summery table of safety monitoring and assessments that will be conducted at every follow-up. The pregnancy test will be conducted before the start of the study and at week 6 (not included in the following table) for pre-menopausal patients.

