## Double Blind Trial Investigating the Role of Sulfasalazine in Decreasing Opioids Requirements in Breast Cancer Patients

History will focus on symptoms of porphyria, intestinal, urinary obstruction, or blood dyscrasias.

- Neuro exam Mini mental state test
- Abd exam Light and deep palpation of the abdomen
- CBC Complete blood count with differential
- BMP Basic metabolic panel with renal function
- LFT Liver function tests
- UA Urinalysis

Finally, blood and urine samples to monitor for side effects from the study medication. The manufacturer of sulfasalazine recommends that blood test be done every two weeks to monitor for side effects. Sulfasalazine may cause anemia and decreased white blood cells. Additionally, it may cause liver and renal damage. Therefore, blood and urine will be collected at every follow up by a phlebotomist who is not part of the study. The collected samples will be labeled by the research team. The blood sample will be used for safety monitoring by analyzing the basic metabolic panel and complete blood count. At the baseline, Week-6, and Week-12, additional blood will be immediately centrifuged and the plasma will be stored in a -80 degrees Celsius freezer for later analysis for inflammatory mediators and tumor markers. The collected urine will be used for urinalysis. Any significant deviation from the baseline values of the CBC, liver function, renal (basic metabolic panel) function, or UA will result in un-blinding of the effected patient, withdrawal from the study, and consultation with the appropriate service.

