## **Double Blind Trial Investigating the Role of Sulfasalazine in Decreasing Opioids Requirements in Breast Cancer Patients**

cultural settings. This questionnaire would be collected at the start of the trial, week 2, week 4, week 6, week 8, week 10 and the end of the 12 week pilot trial.

Finally, patients will be provided with a pain medication log to document the amount of pain medications needed. Subjects will record their opioid pain medication use - both long acting and breakthrough pain. They will be asked to record their opioid pain use daily (both long acting and breakthrough pain meds). In addition, we will also capture data regarding NSAID's, Tylenol and other medications used for pain and document the daily study medication. A research nurse or study coordinator will make weekly calls to the patient to ensure they are taking assigned drug (placebo or sulfasalazine), assess side effects, and recording pain medication use. At the end of study, the drug diary will be collected. Due to the subjective of pain, we chose verified and well accepted surveys that are used in clinical settings to have a more relevant data for better interpretation.

All surveys will be conducted at baseline before starting any treatment. The pain medication log will be done on daily basis. At the end of the study, all data will be gathered and compiled for statistical analysis. The study will be conducted at both the pain clinic at south campus and at the oncology clinic at main campus.

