### **Exclusion Criteria:**

- Patients with intestinal or urinary obstruction or at risk of such disorders.
- History of porphyria
- History of blood dyscrasias, hepatic disease (ALT and AST greater than 2.5X the upper limit of normal).
- History renal disease (serum creatinine greater than 1.5 mg/dl)
- Patients taking Lapatinib or Digoxin.
- No sustained hypercalcemia (blood calcium level greater than 10.4 mg/dl).
- Hypersensitivity to sulfasalazine, its metabolites, sulfonamides, or salicylates.
- The patient is or becomes incarcerated.
- History of addictive behavior, severe clinical depression, or psychotic features.
- Possible pregnancy or lactation.
- Those receiving remuneration for their pain treatment (e.g., disability, worker's compensation).
- Those involved in active litigation relevant to their pain.

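### Safety blood tests justified by a two-weekly recommendation ride on visits with a +/- 1 week window, so two compliant draws can be 28 days apart; a 21-day cap would be a cheap, optional improvement

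*Protocol*

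**What the plan says.** All of this is in the Protocol, Study Description, unless noted.

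- **Visit schedule.** Patients return for "follow ups at 2 weeks (+/- 1 week), 4 weeks (+/- 1 weeks), 6 weeks (+/- 1 weeks"), and then at weeks 8, 10 and 12 with the same tolerance.
- **Reason for the blood tests.** "The manufacturer of sulfasalazine recommends that blood test be done every two weeks to monitor for side effects". The text then names anemia, low white cells, and liver and renal damage as risks, and concludes: "Therefore, blood and urine will be collected at every follow up".
- **Safety table.** It is introduced with "The following is a summery table of safety monitoring and assessments that will be conducted at every follow-up". Only the legend of its rows can be read.
- **Dose.** Sulfasalazine starts at 0.5 g three times a day for one week, "then at a dose of 1 gram three times a day for the remainder of the 3 months".
- **Action on results.** A significant change from baseline in blood count, liver, renal or urine results leads to un-blinding of that patient, withdrawal and referral.
- **Other safeguards.** At visits, "History will focus on symptoms of porphyria, intestinal, urinary obstruction, or blood dyscrasias". Between visits, staff telephone every week and ask about side effects. The Exclusion Criteria remove patients with known blood, liver or renal disease at entry.

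The readable text gives the draws no window of their own and sets no maximum number of days between them.

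**The concern.** The protocol delivers its two-weekly testing through the visits, so the draws inherit the visit window. A tolerance of one week either way is half the interval between visits, and adjacent windows therefore touch. That is harmless for a questionnaire. For a test whose purpose depends on the interval, an early visit followed by a late one can double the interval while every visit is on protocol.

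What is at stake is how soon a silent laboratory change is seen. The un-blind and withdraw rule can act only on a sample already taken. Symptom history and telephone calls do not detect a symptom-free fall in counts or a rise in liver or renal values, and the exclusions apply only at entry. The long gap can also fall at an awkward time: a day 7 draw reflects the starting dose, so a next draw on day 35 leaves the first four weeks at full dose without a blood test.

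**Working it through.** **Inputs** (Protocol, Study Description): targets at weeks 2, 4, 6, 8, 10 and 12, which are days 14, 28, 42, 56, 70 and 84; tolerance w = 7 days; dose step after day 7; cited interval 14 days.

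**1. The plan's own figure.** Each difference between consecutive targets is 14 days (28 - 14, 42 - 28, and so on). The nominal schedule reproduces the two-weekly interval.

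**2. Windows.** Target +/- 7 gives days 7-21, 21-35, 35-49, 49-63, 63-77 and 77-91.

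**3. Longest compliant gap.** With offsets a (earlier visit) and b (later visit), each between -7 and +7, gap = 14 + b - a. The maximum is at a = -7 and b = +7: 14 + 7 + 7 = 28 days, for example day 7 to day 35. Ratio to the cited interval: 28/14 = 2.

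**4. How extreme this is.** In whole days there are 15 x 15 = 225 allowed pairs. One gives 28 days. A gap above 21 needs b - a of at least 8, which gives 7 + 6 + 5 + 4 + 3 + 2 + 1 = 28 pairs; the other 197 give 21 days or fewer. These count what the windows allow. They are not probabilities, because the protocol says nothing about how visits will actually fall.

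**5. No drift.** The windows are tied to fixed targets. The longest possible mean gap between the six follow-up draws is (91 - 7)/5 = 16.8 days. Two gaps above 21 days cannot follow each other: the offset would have to rise by at least 8 + 8 = 16, and its whole range is 14.

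**6. First draw.** It falls at most 21 days after treatment starts, which is 21 - 7 = 14 days after the dose doubles. The readable text does not say how long before the first dose the baseline blood is taken, so the gap from baseline draw to first follow-up draw cannot be worked out.

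**7. Can a 21-day cap be met within the present windows?** The next target lies 14 - a days after a visit with offset a. Since a is at least -7, this is at most 14 + 7 = 21 days. Booking the next visit by its target day therefore always meets the cap. In general, a visit k days early limits the next one to at most 7 - k days late; an on-time or late visit imposes no limit beyond the existing window.

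**The case against.** The strongest reply is that the protocol does what it says: every nominal gap is 14 days, the tolerance is there for patients in moderate to severe pain seen at two clinics, and fixed targets keep the mean gap at 16.8 days or less. All of that stands. So a reader might infer that the plan contradicts the manufacturer's recommendation, or that patients would routinely go four weeks untested, but the text supports neither. The schedule follows the recommendation, and 28 days arises only when the earliest allowed visit is followed by the latest.

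Second, 21 days is not two weeks either, and the protocol does not say what tolerance the manufacturer accepts. This also stands. Nothing in the document shows that 28 days is unsafe or that 21 is safe. The cap is a proposed tolerance, chosen because it halves the excess over 14 days (from 14 days to 7) and fits the existing windows.

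Third, the safety table may hold a limit. Its grid is lost to the reader, so it would be wrong to say that the plan sets none. The sentence that introduces it repeats only that the assessments take place at each follow-up.

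Fourth, weekly calls, visit history and examination, and entry exclusions reduce the risk. They do, for symptoms and for known disease. They do not replace a test for silent changes, so they narrow the point without removing it.

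**Conclusion.** The point holds in a limited form. As readable, the rule allows consecutive safety draws up to 28 days apart, twice the interval given as the reason for drawing them, and the gap can cover the first four weeks at full dose. This is the limit of compliant scheduling; how often it would occur cannot be known from the document. The conclusion assumes that safety draws take place on the visit day, as the text states, and that the unreadable table sets no separate limit.

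It is an optional, inexpensive safety improvement. A reader might take it as a threat to the trial's result, but the timing rule is the same in both blinded arms and has no effect on their comparison.

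**What to change.** Keep +/- 1 week for the clinic and survey visits. Add a rule to the paragraph on blood and urine samples in the Study Description, for example: *Consecutive safety draws will be no more than 21 days apart. After an early visit, the next visit will be booked no later than its target day; if it is missed or delayed beyond 21 days from the last draw, a lab-only draw will be taken.* The investigators should confirm the 21 days against the two-weekly recommendation. If the safety table already states a limit, the text should simply refer to it.

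The cost is one short addition to the protocol, somewhat less freedom in booking after an early visit, and an occasional lab-only trip for patients in pain, in both arms because the trial is blinded. Patients who keep to the booking rule need no extra procedure. Endpoints, randomization and sample size are unchanged.

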In terms of the blood analysis for inflammatory mediators, ten milliliter blood sample will be collected at the baseline visit, week 6 and at the end of the study (week 12) for all enrolled patients. These three time points will allow us to understand the temporal effect of sulfasalazine on inflammatory mediators. The mid-time point will allow us to maximize the data extraction in case so patients may wish to quit the study before week 12. All samples will be collected from the antecubital fossa. The blood samples will be spun at 12,000 RVM for 10 minutes and the serum will be stored in -80 degree Celsius freezer until analyzed. We will utilize commercially available enzyme-linked immunosorbent assay (ELISA) kits to measure the inflammatory mediators IL-6, and TNF-alpha. Glutamate will be measured using Amplex Red Glutamic Acid Oxidase Assay kit. Additionally, we will measure tumor markers for breast cancer including CA 27.29 and CEA using commercially available ELISA kits, we will also collect tumor measurements from standard of care PET scans to evaluate the tumor size.

The data will be analyzed when all participants complete the trial. At that point we will unblind the subjects and finalize the data analysis.

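### Examination and laboratory triggers open the treatment code automatically, although no stated next step depends on the arm and no recipient of the code is named

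*Protocol*

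**What the plan says.** All the relevant text is in the Protocol, Study Description.

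- **Who holds the code (randomization paragraph).** "The assignment of patients will be revealed only to the pharmacist". The pharmacist neither communicates with patients nor analyses data. The blind is promised in these words: "Neither the patients nor the treating physicians will know into which group individual patients will be assigned".
- **Examination trigger (follow-up paragraph).** A Mini Mental State test and abdominal palpation are done at each of six follow-ups. "Any deviation from the normal limits will result in un-blinding the effected patient (to elucidate whether he/she is a control or a treatment group". The same rule also takes the patient out of the trial in either arm, and imaging and, if indicated, a surgical consultation follow when an obstruction is suspected.
- **Laboratory trigger (blood and urine paragraph).** For blood count, liver, kidney and urine results, a change from baseline judged significant "will result in un-blinding of the effected patient, withdrawal from the study, and consultation with the appropriate service". Samples are taken at every follow-up. The same paragraph lists anemia, low white cells, and liver and renal damage as possible effects of sulfasalazine.
- **Planned unblinding (last paragraph of the section).** "The data will be analyzed when all participants complete the trial. At that point we will unblind the subjects".

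No sentence says who is told the assignment when a trigger opens it.

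**The concern.** Both triggers carry a mandatory code break. A code break is usually tied to a need: someone caring for the patient has to know what she is taking. Here it follows from the finding itself, whether or not anyone needs the answer. The patient is withdrawn in either arm, and imaging and consultation are described without reference to the arm.

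What is at stake is mainly the blind for the patients who remain. The primary objective is opioid use; the secondary objective is pain and quality of life. All three are reported by patients or recorded with the help of staff who see them at visits and telephone them weekly about side effects and pain medication. The drug has recognised laboratory effects. Staff who repeatedly see a finding paired with a revealed assignment can learn which findings point to active drug and guess the arm of other patients. That could colour opioid decisions, the weekly calls and the recording of use.

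A smaller, direct route also exists. Surveys are collected at the visits where the examination is done, and no order is stated. A triggered patient's surveys for that visit, and any diary collected as she leaves, could be completed or collected after her assignment is known. At week 12 that is the visit supplying the final data.

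**Working it through.** The protocol states no figure on this point, so there is none to reproduce. The check is a comparison of the text, followed by an illustration of scale.

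**Does any stated action depend on the arm?**

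| Step after a trigger | Where stated | Conditional on arm? |
|---|---|---|
| Withdrawal | Examination and laboratory paragraphs | No |
| Imaging and surgical consultation | Examination paragraph | No: on suspected obstruction, and on indication |
| Consultation with the appropriate service | Laboratory paragraph | No |
| Code break | Both paragraphs | Not applicable; automatic |

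The only reason given for the code break is to find out the arm. No later sentence uses the answer.

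**Is it consistent with the blind?** The randomization paragraph restricts the assignment to the pharmacist and contains no exception. The trigger paragraphs require it to be opened, and the pharmacist does not deal with patients. To serve any purpose in the patient's care, an opened code has to pass to someone else. The protocol neither names that person nor excludes staff who see other participants at the same two clinics.

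**Scale (illustration only).** Inputs from the protocol: 40 patients and 6 follow-ups (weeks 2, 4, 6, 8, 10, 12), so 40 × 6 = 240 patient-visits at which a trigger can occur. Assumed, because the protocol gives nothing: a per-visit trigger probability p, constant, independent across visits and equal in both arms.

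Chance that a patient's code is opened = 1 − (1 − p)^6. Expected code breaks = 40 × that chance.

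| p per visit (assumed) | 1 − (1 − p)^6 | Expected among 40 |
|---|---|---|
| 1% | 0.059 | 2.3 |
| 2% | 0.114 | 4.6 |
| 3% | 0.167 | 6.7 |
| 5% | 0.265 | 10.6 |

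At p = 1%, the chance of at least one code break in the trial is 1 − 0.99^240 = 0.91.

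**An upper check on the assumed range.** Enrolling 20 per group for 16 evaluable allows a loss of 1 − 16/20 = 20%. Since every trigger also withdraws the patient, triggers alone would use that allowance at p = 1 − 0.80^(1/6) = 0.037. The 5% row is therefore already beyond what the sample size provides for.

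**The case against.** The best defence is that these are individual safety code breaks, an ordinary exception to a general blind. A service assessing anemia or a liver abnormality in a drug known to cause both could well want the assignment, and the laboratory rule puts unblinding and consultation in one sentence. This stands in part. A reader might infer that the code break has no use at all; the text does not support that, since a purpose is given in form and a consultant could use the answer. What remains is that no stated step depends on the arm and that the code is opened even when nobody asks for it.

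A reader might also infer that the treating physicians' blind is eroded throughout the trial. The protocol does not say that clinic staff receive the code; it is silent on the recipient. The route to other patients is conditional: staff would have to be told, see a pattern in a few cases, guess other arms and act on the guess. Some guessing from laboratory values is possible without any code break, and how much the released assignments add is not shown. Patients still in the trial remain blind and complete their own surveys and log.

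Nor does the end-of-trial statement, "At that point we will unblind the subjects and finalize the data analysis", prove a contradiction. It describes unblinding for the analysis and can coexist with individual safety code breaks. The tension is with the pharmacist-only rule and the physicians' blind.

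Finally, one might take trigger rates above 5% and conclude that a large share of the trial is unblinded. Those rates would be assumed, they count code breaks rather than biased outcomes, and at that level loss of patients becomes the larger problem. Prediction of later assignments from released codes would need a blocked list, which the protocol does not state.

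**Conclusion.** The point holds in a limited form. The protocol makes a code break automatic on any examination finding outside normal limits and any significant laboratory change from baseline, ties no stated action to the result, and does not say who receives it, while promising a pharmacist-only code and blinded treating physicians. These passages need to be reconciled.

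The size of any bias is unknown. It depends on trigger rates, recipients and blocking, none of which is given. About 2 to 11 code breaks among 40 patients, under an assumed 1% to 5% per visit, shows only that some code breaks are likely in a small trial with outcomes open to expectation. The change is worth making because it is cheap and because no analysis can restore a blind once broken. Nothing here concerns whether the triggers or the withdrawal rule are right.

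**What to change.** In Study Description, reconcile the randomization, examination and laboratory paragraphs by separating the code break from the safety response.

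1. Leave the triggers, withdrawal and consultation as the sponsor sets them.
2. Replace automatic unblinding with a rule that the code is opened only when those caring for the patient state that the assignment is needed for her care.
3. Have the pharmacist release it only to those who need it and, where possible, not to staff who assess, call or collect surveys from other trial patients.
4. Have the pharmacist log the date, reason and recipients of each release.
5. Where the situation allows, collect that visit's surveys and log before the code is opened.
6. In the randomization paragraph, name this as the exception to the pharmacist-only rule.

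The cost is protocol wording and a log kept by the pharmacist, who already holds the code. The downside is one extra step to obtain the assignment. Full separation may also be impossible when the service caring for the patient sees other trial patients, which is likely enough at two shared clinics; the log then at least records who was told and when.

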### **Inclusion Criteria:**

- Adult patients aged >18 and 95< year old.
- Diagnosis of cancer with 3-day average numeric pain rating score (NPRS) for pain of at least 5/10 at baseline evaluation.
- On opioid regimen for at least 3 weeks. This time frame will allow patients to have a stable opioid regimen as it typically takes a few weeks of titration of opioids to reach

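### The examination trigger for un-blinding and withdrawal has no baseline or significance qualifier, and both safety triggers end study participation rather than study drug, so later opioid-log data would by inference be lost

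*Protocol*

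**What the plan says.** Protocol, Study Description, follow-up paragraph: a Mini Mental State test and abdominal palpation are done at each of the six follow-up visits (weeks 2 to 12, each within one week either way). The rule then reads "Any deviation from the normal limits will result in un-blinding the effected patient". The same sentence gives the purpose of the code-break as learning the arm, and takes the patient out of the study altogether. The next sentence shows the harm in view: "If intestinal or urinary obstruction is suspected, the appropriate imaging studies will be conducted".

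Protocol, Study Description, blood and urine paragraph: the laboratory rule has the same double consequence but a narrower trigger, "Any significant deviation from the baseline values of the CBC, liver function" and the other listed tests. The same paragraph says "Sulfasalazine may cause anemia and decreased white blood cells", and names liver and renal damage as possible effects.

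Protocol, Inclusion and Exclusion Criteria: screening touches these examinations only in part. Excluded are "Patients with intestinal or urinary obstruction or at risk of such disorders" and "History of addictive behavior, severe clinical depression, or psychotic features". No criterion sets a Mini Mental State score or a normal abdomen at entry. The age criterion is "Adult patients aged >18 and 95< year old", and at least three weeks on opioids is required.

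Protocol, Brief Summary and Study Description: the primary objective is opioid use over 12 weeks, measured by a daily patient log and supported by weekly calls. The Brief Pain Inventory is given at entry and at the end. Enrolment is 20 per arm so that 16 are evaluable.

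**The concern.** The protocol qualifies one safety trigger and leaves the other unqualified, although both lead to the same irreversible step. The examination trigger compares the patient with normal limits, not with his or her own starting point. In patients who may be elderly, have cancer and are already on opioids, an imperfect Mini Mental State score or a long-standing abdominal finding can be present at randomisation. Such a patient meets the trigger at week 2 although nothing has changed.

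The second part concerns the primary outcome. A patient who leaves the study, rather than only stopping the capsules, has no planned log, calls or surveys afterwards. Cognitive and abdominal findings plausibly relate to opioid dose, which is the outcome. The laboratory triggers include effects that the protocol itself attributes to sulfasalazine. The patients whose records are cut short may therefore differ from the rest, and may differ by arm. Enrolling 20 to obtain 16 covers a loss of numbers, not a loss of this kind. The code is also broken for findings that may need no action, in a trial whose outcome is self-reported.

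**Working it through.** **The two rules side by side**

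| | Examination rule | Laboratory rule |
|---|---|---|
| Reference | normal limits, not defined | patient's baseline |
| Significance required | no | yes |
| Consequence | un-blinding, leaves study | un-blinding, leaves study |
| Normal result required at entry | no | in part (liver enzymes, creatinine, calcium, blood dyscrasias) |

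**Log weeks lost after a trigger.** For a trigger at nominal week w, weeks lost = 12 − w. The window of one week either way moves each figure by up to one week.

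| Trigger visit | Weeks lost (nominal) | Share of 12 | Range with window |
|---|---|---|---|
| 2 | 10 | 83% | 9–11 |
| 4 | 8 | 67% | 7–9 |
| 6 | 6 | 50% | 5–7 |
| 8 | 4 | 33% | 3–5 |
| 10 | 2 | 17% | 1–3 |
| 12 | 0 | 0% | 0–1 |

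Log data before the trigger are not affected.

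**The plan's allowance.** 20 enrolled and 16 needed implies a loss of 4/20 = 20%, and 16/(1 − 0.20) = 20 reproduces the stated enrolment.

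**Illustration (a): new findings, independent across visits.** The protocol gives no trigger rate, and the text does not define evaluable, so both are assumptions. Suppose a trigger at any of the first k follow-up visits leaves too few log weeks, and there are no other losses. The per-visit rate p that in expectation uses up the allowance solves (1 − p)^k = 16/20, so p = 1 − 0.8^(1/k):

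- all 12 weeks needed, k = 5: 4.4%
- 10 weeks suffice, k = 4: 5.4%
- 8 weeks suffice, k = 3: 7.2%
- 6 weeks suffice, k = 2: 10.6%
- 4 weeks suffice, k = 1: 20%

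**Illustration (b): findings present from entry.** These are not independent across visits; all trigger at week 2. Planned log time per arm is 20 × 12 = 240 patient-weeks. With n such patients the loss is 10n/240: 4.2% for n = 1, 8.3% for n = 2, 16.7% for n = 4. Four such patients use the whole allowance if two weeks of log are not evaluable.

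Neither illustration estimates what will happen. They show what trigger frequency would matter.

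**The case against.** The strongest reply is that this is loose wording around a sound safety rule. Normal limits are undefined, the next sentence concerns suspected obstruction, patients with or at risk of obstruction are excluded, and a sensible investigator would not withdraw someone for an unchanged finding. Full withdrawal on a safety signal is also a cautious choice in a small pilot that expects non-completers. The aim is indeed harm detection. But an investigator who spares the stable patient departs from the text, and the laboratory rule shows that better wording was available.

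It can also be said that no sentence stops the log after withdrawal. That is correct: the data loss is inferred from leaving the study and from the absence of any described follow-up. The week-6 blood sample is justified partly by early leavers, but it covers blood only. A SAP could say how incomplete logs are analysed; it could not recover entries that were never made.

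A reader might infer three stronger points that the document does not support.

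- *That the early code-break contradicts the plan to un-blind when all participants complete.* That passage concerns un-blinding for analysis and does not say it is the only occasion. Individual safety code-breaks are expressly planned exceptions.
- *That the log up to the trigger is lost because the diary is collected at the end of study.* Survey measures are collected at every follow-up, four surveys are announced, and the log can be read as the fourth. The weekly calls also cover pain medication use.
- *That the rule biases the comparison in a known direction.* With no trigger rate by arm, neither direction nor size can be derived.

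**Conclusion.** The point holds as a low-cost improvement. Three things rest on the text directly: the examination trigger lacks the qualifier that the laboratory trigger has; eligibility does not require a normal examination; and both rules take the patient out of the study. It follows, on a literal reading, that a stable pre-existing finding ends participation at the first follow-up.

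The loss of later primary-outcome data is an inference, though nothing in the text contradicts it. It amounts to nominally 10 of 12 log weeks for a week-2 trigger (9 to 11 with the window) and less for later ones. The break-even rates of 4.4% to 20% per visit depend on what counts as evaluable and on no other losses. That the loss may be informative is plausible; how often it occurs, and which way it would act, is unknown. Confidence is medium.

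**What to change.** 1. Make the examination trigger a clinically significant change from the patient's own baseline, with the threshold set by the sponsor's clinicians. Record both examinations at baseline if the safety table, whose visit grid is not visible, does not already do so.
2. In both the examination and the laboratory rule, replace leaving the study with discontinuation of study drug. Continue the log, weekly calls and surveys to week 12 for patients who agree, and analyse them in their randomised arm. As a clarification only, state that the log to date is collected at the trigger visit.
3. Break the code only when clinical care needs it, and keep the result from those who collect outcomes. Flag all data after un-blinding and run a sensitivity analysis without them.

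The cost is protocol wording, possibly one baseline entry, further contacts with patients off drug, and one sensitivity analysis. Sample size does not change.

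The downsides should be accepted openly:

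- Off-drug time dilutes the contrast. If a share p of patients still on drug triggers at each visit (examination and laboratory combined, an assumption), the share of planned log time off drug is the sum over i = 0 to 4 of p(1 − p)^i × (10 − 2i)/12. This is 5%, 12% and 22% at p = 2%, 5% and 10%. It is a share of time, not a bound on the change in effect.
- Opioid use after the event may change for other reasons, such as a dose cut for impaired cognition or surgery for obstruction, and could move the contrast either way.
- Self-report after un-blinding is weaker evidence.
- A self-completed log may be unreliable in a patient with new cognitive impairment; the weekly call would help only in part.

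A baseline-referenced trigger should reduce how often these arise, and fewer code-breaks should reduce the third.
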